### **List of abbreviations and relevant definitions**

ED	Emergency Department
UMCG	University Medical Centre of Groningen
APOP	Acutely Presenting Older Patient
MRI	Magnetic resonance imaging
CT	Computed Tomography
Qcsa	Cross-sectional area
CFS9	Clinical Frailty Scale
METC	Medical research ethics committee (MREC); in Dutch: medisch ethische toetsing commissie (METC)
Sponsor	The sponsor is the party that commissions the organisation or performance of the research, for example a pharmaceutical company, academic hospital, scientific organisation or investigator. A party that provides funding for a study but does not commission it is not regarded as the sponsor, but referred to as a subsidising party.
WMO	Medical Research Involving Human Subjects Act (in Dutch: Wet Medisch-wetenschappelijk Onderzoek met Mensen)
LOS	Length of stay
ITU	Intensive therapy unit
eCRF	Electronic consent form
REDCap	Research electronic Data Capture

### 3. ABSTRACT (max. 250 words)

- **Background**

Older people visit the ED more frequently than younger people and have a higher risk of functional decline, ED revisit or death. Several screening tools (such as VMS and APOP) have been developed to identify patients at the highest risk of adverse outcomes. Almost all require adequate communication with the patient, which is not always possible, for example when elderly patients present with a delirium. Point of Care Ultrasonography (POCUS) may be a valuable alternative screening tool in these instances.

- **Main research question**

To identify whether POCUS measurement of the rectus femoris muscle cross-sectional area (Qcsa) can be used as an alternative screening tool to predict functional decline, ED revisit or death in elderly patients in the ED.

- **Design (including population, confounders/outcomes)**

This is a single centre prospective trial. Patients >70 years and older presenting in the ED of the UMCG hospital who are participating in the Acutelines bio-databank are eligible for inclusion. 68 patients will be included. Data will be extracted from the Acutelines bio-databank. A trained physician will perform ultrasound measurements in a standardized way.

- **Expected results**

The aim of this study is to evaluate whether ultrasound measurements of the Qcsa can be utilized to identify older patients who are at risk for functional decline, ED revisit or death.

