POCUS has been shown to be a promising technique to measure skeletal muscle mass [12]. It is non-invasive, can be performed at the bedside and has an excellent intra-class correlation coefficient for intra- and inter-observer agreement. [13, 14] Recent studies in a subgroup of hospitalized patients have shown that Qcsa measurements can predict readmission and mortality [15, 16]. ED data however are scarce: Shah et al found in a subset of elderly trauma patients that ultrasound measurements of biceps and quadriceps had modest concordance with the Clinical Frailty Scale (CFS9) [17], whereas Benton et al demonstrated that ultrasound measurements of sarcopenia in older non-trauma patients were (to a variable extend) associated with frailty, falls and subsequent hospitalizations [18].

As POCUS measurement of Qcsa is independent of patient effort and functional or cognitive impairment, it has the potential to be a valuable (alternative) screening tool for functional decline

and mortality in older patients in the ED. However, until now, no data have been published about the relation between Qcsa and functional outcome for patients presenting in the ED.

The aim of this study is to evaluate whether ultrasound measurements of the Qcsa in the ED may be utilized to identify older patients who are at risk for functional decline, ED revisit or death. Our study hypothesis is that Qcsa measurements can predict functional decline, ED revisit or death of older ED patients.

- **Research question**

Primary objective

To evaluate:

- The relation between POCUS measurements of the Qcsa in patients >70 presenting in the ED and ED revisit or death within three months and functional decline within twelve months of their ED visit. Functional decline in this respect is defined as at least one point increase in the Katz ADL-6 survey score or new institutionalization (higher level of assisted living) within twelve months after ED visit.

Secondary objectives

To evaluate:

- To compare the ability of the Qcsa ultrasound to predict functional decline, ED revisit or death in older patients in the ED to the APOP questionnaire (gold standard).
- To compare the added value of Qcsa ultrasound to the APOP questionnaire in the prediction of functional decline, ED revisit or death in older patients in the ED.
- To evaluate the relation between Qcsa ultrasound and physical activity (as scored by KATZ ADL-6 questionnaire).

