## 5.9 Data analysis

 
Justification of sample size (e.g. power analysis)
 

The sample size is calculated based on functional decline and mortality in elderly visiting the ED. We defined functional decline as at least one point increase in the Katz ADL-6 survey score or new institutionalization (higher level of assisted living) within twelve months after ED visit. Prior research in the Netherlands found 9,5% of patients aged <math>\geq 70</math> year died within three months after ED visit and 30,6% experienced functional decline or mortality at 90-day follow-up [8]. With an assumed prevalence of the composed endpoint of 30%, 54 patients are needed to be able to confirm a diagnostic test accuracy with a sensitivity and specificity of <math>>0.8</math> each for a predefined Qcsa cut-off value with a power of 90% and an alfa error of 0.05. To allow for loss of follow-up, 25% more patients will be recruited, resulting in a sample size of 68 patients.

 
Statistical analysis
 

Continuous variables are expressed as mean (95% CI) when normally distributed and median with interquartile range when not normally distributed. Categorical data are presented as absolute

numbers and percentages.

There is a difference in muscle mass between man and woman. The ultrasound measured Qcsa will therefore be adjusted for sex by multiplying female Qcsa with the coefficient 1.484 (male=1) prior to analysis [15]. Diagnostic accuracy of QCSA will be presented as sensitivity and specificity of the optimum Qcsa cut-off point to separate cases (primary endpoint reached after three or twelve months) from non-cases. This optimum cut-off point is calculated as the maximum sum of sensitivity + (1-specificity) using ROC statistics (under the condition of equal costs of misqualification).

A logistic regression model will be used to evaluate whether individual Qcsa predicts functional decline, ED revisit or death. Age, comorbidity, Katz ADL-6, known dementia are defined as clinically relevant covariates and will be included in the regression model.. The predictive ability of the multivariable risk prediction models (e.g. Qcsa prediction model vs APOP prediction model) will be compared.  $\chi^2$  values will be calculated for each prediction model.

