A 2-sided P-value <0.05 will be considered statistically significant. Missing data are reported in the results section according to the STROBE 2015 guideline. All statistical analyses will be performed using R or SPSS 26.0 software.

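### The Qcsa-APOP comparison has no estimate of the difference and no rule that could support calling Qcsa comparable to APOP

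*Combined protocol and SAP*

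**What the plan says.** Section 3 (Abstract) puts the main question as whether Qcsa "can be used as an alternative screening tool to predict functional decline, ED revisit or death in elderly patients in the ED". Just before that, it gives the setting, which is patients with whom communication fails: "Point of Care Ultrasonography (POCUS) may be a valuable alternative screening tool in these instances".

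The hypothesis in section 4 concerns Qcsa alone: "Our study hypothesis is that Qcsa measurements can predict functional decline, ED revisit or death of older ED patients". The first secondary objective is comparative. It sets out "To compare the ability of the Qcsa ultrasound to predict functional decline, ED revisit or death in older patients in the ED" against the APOP questionnaire, which is labelled the gold standard.

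Section 5.9 covers the comparison in two sentences. The first is: "The predictive ability of the multivariable risk prediction models (e.g. Qcsa prediction model vs APOP prediction model) will be compared". The second says that a chi-square value will be calculated for each model. The only inferential threshold in the analysis text is general: "A 2-sided P-value <0.05 will be considered statistically significant". The section names no measure of the Qcsa-APOP difference, no paired method, no margin and no rule for drawing a conclusion.

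The sample-size paragraph of 5.9 also names an absolute target, sensitivity and specificity each above 0.8 at a predefined cut-off.

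**The concern.** A chi-square value for each model describes how well that model fits. It does not give the size or the uncertainty of the difference in discrimination between two models with different predictors. A two-sided 0.05 threshold, if applied to such a difference, can show that one tool is better. It cannot show that Qcsa is acceptably close to APOP.

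With about 16 cases, a non-significant comparison is the likely result even if Qcsa is moderately worse. Because the plan does not say how that result will be interpreted, a reader or author could take it as support for Qcsa as an alternative. Qcsa might then be accepted although it misses more at-risk patients than the questionnaire.

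**Working it through.** **Inputs from section 5.9.** Prevalence 30%; 54 evaluable patients, 68 recruited; power 90%; alpha 0.05; sensitivity and specificity above 0.8.

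**Assumed, because the documents give no values.** APOP AUC 0.75 or 0.80; correlation between the two scores 0.2, 0.5 or 0.8; normally distributed scores in cases and non-cases; paired DeLong test.

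**1. The plan's own sample size.** The null value is not stated. With an assumed null of 0.50, a one-sided 0.05 and the variance taken at 0.80:

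- cases = (1.645 + 1.282)² × 0.80 × 0.20 / (0.80 − 0.50)² = 15.2, so 16
- N = 16 / 0.30 = 53.3, so 54
- 54 × 1.25 = 67.5, so 68

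The 54 and 68 are therefore reproduced, and they size an absolute accuracy statement about Qcsa. The APOP comparison does not enter. Of 54 patients, 30% gives 16 cases and 38 non-cases.

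**2. Chance of a non-significant difference when Qcsa is truly worse.** For each AUC, the case and non-case means are separated by √2 × Φ⁻¹(AUC). Simulated studies had 16 cases and 38 non-cases and were tested at two-sided 0.05.

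| APOP AUC | Score correlation | Qcsa 0.10 lower | 0.15 lower | 0.20 lower |
|---|---|---|---|---|
| 0.75 | 0.2 | 0.82 | 0.70 | 0.50 |
| 0.75 | 0.5 | 0.76 | 0.56 | 0.33 |
| 0.80 | 0.2 | 0.80 | 0.66 | 0.46 |
| 0.80 | 0.5 | 0.74 | 0.52 | 0.30 |
| 0.80 | 0.8 | 0.52 | 0.19 | 0.04 |

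Repeat runs for the 0.10 deficit gave 0.76 to 0.83 at correlation 0.2-0.5 and 0.51 to 0.56 at 0.8.

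**3. Sensitivity to the inputs.**

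- With 54 to 68 patients and correlation 0 to 0.5, a 0.10 deficit is detected in 15-30% of studies, so it is missed in 70-85%.
- At 50% prevalence it is detected in 15-37%, so it is missed in 63-85%.
- On sensitivity alone (0.60 against 0.80 among 16 to 20 cases), the deficit is detected in 11-19% of studies by the exact McNemar test and in 19-30% by its mid-p version.

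**4. What the interval could show if the tools were truly equal.** At correlation 0.2-0.5 the mean 95% half-width of the AUC difference is 0.136 to 0.183, so SE = half-width / 1.96 = 0.069 to 0.093. For an illustrative loss of 0.10:

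- P(lower limit > −0.10) = P(Z > 1.96 − 0.10/SE), which is 0.30 at the smaller SE and 0.19 at the larger
- At correlation 0.8 (APOP AUC 0.80) the half-width is about 0.09, so SE = 0.046 and the probability is P(Z > 1.96 − 2.18) = 0.59

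**5. Size that a 0.10 margin would need.** This uses the Hanley-McNeil variance V with both AUCs at 0.75, 30% prevalence and one-sided 0.025. The variance of the difference is 2V(1 − r), where r is the correlation between the AUC estimates. For r from 0.5 down to 0, 80% power needs 254 to 506 evaluable patients and 90% power needs 339 to 677. At a margin of 0.15 the figures are 114 to 226 and 152 to 302.

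**The case against.** The main question does not name APOP. Sections 3 and 4 introduce Qcsa as an alternative for patients with whom a questionnaire cannot be completed. The hypothesis and the primary objective concern Qcsa's own relation to outcome, and the APOP comparison is secondary. On that view, non-inferiority to APOP is not the test of the main question. This stands. However, section 5.3 does not restrict inclusion to such patients, and section 4 makes APOP the comparator, so the study will produce a head-to-head result that has to be interpreted.

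A reader might infer that the plan intends to declare Qcsa an alternative when the comparison is non-significant, or that two-sided 0.05 is its only stated criterion. The documents support neither. The 0.05 level is general and is not tied to a Qcsa-APOP difference test, and no sentence equates non-significance with comparability. The plan also names the above-0.8 accuracy target. That target belongs to the sample size, refers to a predefined cut-off and is not relative to APOP. The analysis instead reports accuracy at an optimum cut-off derived from the data and does not make 0.8 a success rule.

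It is also too strong to say that any clearly worse Qcsa would usually escape detection. That is secure for a deficit of about 0.10, less so at 0.15 and not at 0.20. Finally, the simulation compares two single scores, while 5.9 compares multivariable models. If those models share covariates, which 5.9 leaves open, their predictions could correlate at 0.8 or so, and the miss rates fall as the last row of the table shows.

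**Conclusion.** The concern holds in a limited form. Section 5.9 provides neither an estimate of the Qcsa-APOP difference nor a rule under which comparable performance could be concluded, and it does not rule out reading non-significance as support. The gap affects a secondary objective that bears on the headline wording. The primary objective is not affected.

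With 16 cases and 38 non-cases and an APOP AUC of 0.75-0.80, a true 0.10 deficit goes undetected in about 74-83% of studies at score correlation 0.2-0.5 and in about half at 0.8. A 0.20 deficit goes undetected in about 30-50% and about 5% respectively. The AUCs, correlations and score distributions are assumptions. The absence of an estimate and a decision rule does not depend on them.

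**What to change.** In 5.9, for the Qcsa-versus-APOP objective:

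- Replace the per-model chi-square comparison with the paired AUC difference (Qcsa minus APOP, same patients) and its 95% confidence interval. State which predictors enter each side.
- State that a non-significant difference will not be taken as evidence that Qcsa is an alternative to APOP.
- Rest any claim of comparable performance on the lower confidence limit, set against a largest acceptable loss that the sponsor fixes before seeing the data. Otherwise report the comparison as inconclusive. The 0.10 used above is only an illustration.
- If the intended meaning is usable where APOP cannot be done, say so in section 3 and in 5.9. Base that claim on the lower confidence limits of Qcsa sensitivity and specificity at a fixed cut-off.

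This takes a few sentences and needs no extra patients or data. The cost is candour about precision, since the APOP comparison will probably be inconclusive at this size. The absolute route is also imprecise. With an observed sensitivity of 0.80 in 16 cases, the approximate half-width is 1.96 × √(0.80 × 0.20 / 16) = 0.196, a lower limit near 0.60. With specificity 0.80 in 38 non-cases it is 1.96 × √(0.80 × 0.20 / 38) = 0.127, a lower limit near 0.67.

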## 4. BACKGROUND

- **Introduction and rationale**

Older patients visit the emergency department (ED) more frequently in comparison to younger adults [1,2]. Admittance to the ED is associated with risk of negative health outcomes such as functional decline and mortality (the ultimate form of functional decline) [2,3]. This is partly explained by non-specific disease presentation or the presence of frailty, comorbidities or cognitive disorders, which complicates their ED presentation, diagnosis and management [4-6]. It is important to identify older patients with frailty, who are at the highest risk for negative outcomes, in order to be able to take appropriate measures during hospitalization (e.g. fall prevention, physiotherapy, geriatric consultation). Recently it became mandatory to screen all elderly ED patients for frailty as stated by the Health and Youth Care Inspectorate in the Netherlands.

Several geriatric screening tools have been developed to identify frail geriatric patients in the ED [7]. The Acutely Presenting Older Patient (APOP) tool has already been implemented in several Dutch hospitals [8]. This is a validated instrument to predict risk for functional decline and mortality in older patients within three months of presentation in the ED [8, 9]. Like most of the existing screening tools the APOP relies on adequate communication with the patient (or the patients' caregiver). Unfortunately, not infrequently communication with the patient is impaired in the ED due to trauma, confusion, sickness or pre-existent dementia.

An alternative screening tool, based on measurement of sarcopenia with POCUS may provide valuable information in these instances. Sarcopenia is a syndrome characterized by progressive and generalized loss of skeletal muscle mass and strength with a risk of adverse outcomes such as physical disability, poor quality of life and death [10]. Sarcopenia and frailty are two separate conditions, but they overlap especially in the physical aspects of frailty [11]. Therefore, measuring sarcopenia might help in predicting frailty. MRI and CT are regarded as the gold standard to measure muscle mass but they are inconvenient and impossible to perform in everyday clinical practice, especially in the ED [10].

POCUS has been shown to be a promising technique to measure skeletal muscle mass [12]. It is non-invasive, can be performed at the bedside and has an excellent intra-class correlation coefficient for intra- and inter-observer agreement. [13, 14] Recent studies in a subgroup of hospitalized patients have shown that Qcsa measurements can predict readmission and mortality [15, 16]. ED data however are scarce: Shah et al found in a subset of elderly trauma patients that ultrasound measurements of biceps and quadriceps had modest concordance with the Clinical Frailty Scale (CFS9) [17], whereas Benton et al demonstrated that ultrasound measurements of sarcopenia in older non-trauma patients were (to a variable extend) associated with frailty, falls and subsequent hospitalizations [18].

As POCUS measurement of Qcsa is independent of patient effort and functional or cognitive impairment, it has the potential to be a valuable (alternative) screening tool for functional decline

and mortality in older patients in the ED. However, until now, no data have been published about the relation between Qcsa and functional outcome for patients presenting in the ED.

The aim of this study is to evaluate whether ultrasound measurements of the Qcsa in the ED may be utilized to identify older patients who are at risk for functional decline, ED revisit or death. Our study hypothesis is that Qcsa measurements can predict functional decline, ED revisit or death of older ED patients.

- **Research question**

Primary objective

To evaluate:

- The relation between POCUS measurements of the Qcsa in patients >70 presenting in the ED and ED revisit or death within three months and functional decline within twelve months of their ED visit. Functional decline in this respect is defined as at least one point increase in the Katz ADL-6 survey score or new institutionalization (higher level of assisted living) within twelve months after ED visit.

Secondary objectives

To evaluate:

- To compare the ability of the Qcsa ultrasound to predict functional decline, ED revisit or death in older patients in the ED to the APOP questionnaire (gold standard).
- To compare the added value of Qcsa ultrasound to the APOP questionnaire in the prediction of functional decline, ED revisit or death in older patients in the ED.
- To evaluate the relation between Qcsa ultrasound and physical activity (as scored by KATZ ADL-6 questionnaire).

## 5. METHOD

### 5.1 Description study design

This is a single centre prospective trial conducted in the ED of the UMCG. Data (including APOP, KATZ-ADL) will be collected from elderly patients presenting in the ED, and ultrasound measurements of the Qcsa will be obtained at the same time after consent is obtained for participation in the Acutelines bio-databank. Functional decline, ED revisit and mortality will be evaluated after three and twelve months as per Acutelines protocol.

### 5.2 Design

5.2.1 Mono- or multicenter study	Mono-center study, use of data/biomaterials from Acutelines (de novo biobank)	
5.2.2 Retrospective study (available data/ biomaterials only) or prospective study (data/ biomaterials from [some] participants will be collected in the future).	Retrospective study: yes/no	Prospective study: YES (Acutelines)
Note: while Acutelines is a prospective data/biomaterial collection, additional data may be collected retrospectively.		
5.2.3 Cross-sectional or follow-up study	Cross-sectional study: yes/no	Follow-up study yes/no
All patients are screened in the ED. ED revisit and mortality will be evaluated after three months and functional decline after twelve months.		
5.2.4 Quantitative or qualitative study (click both if mixed-method)	Quantitative study yes/no	Qualitative study yes/no
This is a quantitative study based on Qcsa measurement and screening tool data.		
5.2.4 Pilot study	yes/no	

### 5.3 Population

5.3.1 Inclusion and exclusion criteria	
Inclusion criteria:	
In order to be eligible to participate in this study, a subject must meet all of the following criteria:	

• Age (>70 years)

• Presenting to the ED of the UMCG for one of the following specialties: internal medicine, nephrology, geriatric medicine, oncology, hematology, lung medicine, gastrointestinal/liver medicine, or emergency medicine (non-trauma).

• Consent obtained for participation in the Acutelines bio-databank

	
Exclusion criteria:	

• Unable to obtain ultrasound image of rectus femoris (e.g. amputation, edema)

• Paresis or paralysis of one or both legs

	
5.3.2 Number of participants	

• Target total number of participants: 68

• Target number of UMCG participants: 68

	
5.3.3 Study subjects (tick all that apply)	

• Healthy volunteers

• Patients

	NO YES
5.3.4 Subject classification (tick all that apply)	

• Participants <math>\geq</math> 16 years

• Children between 12 and 16 years (if applicable, written informed consent will be obtained)

	YES NO

from child and both parents - if both have authority, or guardian [or parents/guardian only if incapacitated child])	
• Children < 12 years ( if applicable, written informed consent will be obtained from both parents - if both have authority, or guardian )	NO
5.3.5 Incapacitated adults Participants are incapacitated/ decisionally incompetent adults ( if applicable, written informed consent will be obtained from legal representative )	NO
	YES

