## 8. APPENDICES

### 8.1 Required text for manuscript

"Data/ samples were obtained from the Acutelines data-, image and biobank [reference 3]. Acutelines is a prospective biobank including patients with a broad spectrum of acute conditions, aiming to facilitate interdisciplinary research on etiology and development of acute diseases with the aid of systematically collected biomaterials and medical data over various timepoints, both during the course of the patient's disease and after recovery. A deferred consent procedure (by proxy) is in place to allow the collection of data and biomaterials prior to obtaining written consent. Clinical data, imaging data and biomaterials (i.e. blood, urine, feces, hair) are collected for patients presenting to the Emergency Department (ED) with a broad range of acute disease presentations. Bedside monitoring data (i.e. electrophysiological waveforms, vital parameters) are automatically captured and stored, and information from other data sources (such as the electronic health records of the hospital-, emergency medical services- and the general practitioner, the municipal registration, health insurance companies and the pharmacy) is securely imported. Follow up data are collected for all included patients during the first 72-hours of their hospitalization and 3-months, 1-year, 2-years and 5 years after their ED visit."

"Biomaterials were collected if the participant had an orange or red triage-color, or was admitted because of sepsis, pneumonia or shock. Sepsis was defined based on the physician's suspicion, sepsis-2 or sepsis-3 criteria. Pneumonia was defined based on radiological evidence of pneumonia combined with the physician's suspicion of a pneumonia. Shock was defined as hypotension (systolic blood pressure < 90 mmHg or a decrease of > 40 mmHg compared to pre-existent) in combination with tachycardia (heart rate > 100 beats/minute).

Study data were collected and managed using REDCap electronic data capture tools hosted at [YOUR INSTITUTION].1,2 REDCap (Research Electronic Data Capture) is a secure, web-based software platform designed to support data capture for research studies, providing 1) an intuitive interface for validated data capture; 2) audit trails for tracking data manipulation and export procedures; 3) automated export procedures for seamless data downloads to common statistical packages; and 4) procedures for data integration and interoperability with external sources."

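### A successful scan is a condition of eligibility, so accuracy will be known only for scannable patients and usefulness as a general ED screening tool may be overstated by an amount the study cannot show

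*Combined protocol and SAP*

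**What the plan says.** Section 5.3.1 lists as an exclusion "Unable to obtain ultrasound image of rectus femoris (e.g. amputation, edema"), next to paresis or paralysis of a leg. The two conditions named are examples, so the criterion covers an unobtainable image for any reason. The same section sets "Target total number of participants: 68". Section 5.1 places the ultrasound after consent to the Acutelines bio-databank.

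The abstract asks whether Qcsa "can be used as an alternative screening tool to predict functional decline, ED revisit or death in elderly patients in the ED". Section 4 explains that communication with the patient is often impaired in the ED and continues: "An alternative screening tool, based on measurement of sarcopenia with POCUS may provide valuable information in these instances". It gives the reason for preferring ultrasound in these words: "As POCUS measurement of Qcsa is independent of patient effort and functional or cognitive impairment". A secondary objective compares prediction of functional decline, ED revisit or "death in older patients in the ED to the APOP questionnaire (gold standard").

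On analysis, Section 5.9 states: "Diagnostic accuracy of QCSA will be presented as sensitivity and specificity of the optimum Qcsa cut-off point". It adds 25% to the sample size for loss to follow-up and says that missing data will be reported under a named reporting guideline. It does not mention failed scans. Section 8.1 says of Acutelines: "Follow up data are collected for all included patients during the first 72-hours of their hospitalization and 3-months, 1-year".

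**The concern.** Failure to obtain an image is one of the possible results of the test under study. When it is an exclusion criterion, a patient who meets every inclusion criterion and has consented can leave the study because of the test's own result. The share of patients with a usable result is then 100% by construction, whatever happens at the bedside.

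Ultrasound is put forward because it should give an answer where a questionnaire cannot. How often it gives no answer is part of whether it can serve as a screening tool, and the plan neither counts nor analyses this. The missing-data statement does not help, because an excluded patient is not a participant with missing data.

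A reader of the final report could apply the published sensitivity and specificity to all older ED patients when they hold only for those who can be scanned.

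**Working it through.** **Inputs.** From the plan: 68 participants (Section 5.3.2); 54 evaluable patients, 30% prevalence, sensitivity and specificity above 0.8, and 25% for loss to follow-up (Section 5.9). Assumed, because the documents give no figure: a failure rate f of 5%, 10% or 15%, equal in cases and non-cases, and sensitivity = specificity = 0.80 among scanned patients.

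**Step 1: the plan's own figure.** 54 × 1.25 = 67.5, rounded up to 68. This step reproduces. The whole allowance is for loss to follow-up, with nothing for failed scans. The 54 itself cannot be checked because no null value is stated; that does not affect this point.

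**Step 2: accuracy with failed scans in the denominator.**

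- Failure counted as not flagged: sensitivity = 0.80 × (1 − f); specificity = 0.80 × (1 − f) + f.
- Failure counted as flagged: sensitivity = 0.80 × (1 − f) + f; specificity = 0.80 × (1 − f).

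| f | Not flagged: sensitivity / specificity | Flagged: sensitivity / specificity | Usable result |
|---|---|---|---|
| 0% | 0.80 / 0.80 | 0.80 / 0.80 | 100% |
| 5% | 0.76 / 0.81 | 0.81 / 0.76 | 95% |
| 10% | 0.72 / 0.82 | 0.82 / 0.72 | 90% |
| 15% | 0.68 / 0.83 | 0.83 / 0.68 | 85% |

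Each convention lowers one measure and raises the other. Under the current design all four rows would be reported as the first.

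**Step 3: unequal failure.** Suppose 20% of cases and 5% of non-cases fail. Overall failure is 0.3 × 0.20 + 0.7 × 0.05 = 9.5%. Not flagged: sensitivity 0.80 × 0.80 = 0.64, specificity 0.80 × 0.95 + 0.05 = 0.81. Flagged: sensitivity 0.64 + 0.20 = 0.84, specificity 0.80 × 0.95 = 0.76. The overall failure rate alone is therefore not enough; the outcomes of these patients are needed too.

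**Step 4: weight of a single patient.** 54 × 0.30 = 16.2, or about 16 cases. If 13 of 16 are detected, sensitivity is 0.81. One further case with a failed scan, counted as not flagged, gives 13/17 = 0.76.

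**Step 5: recruitment.** Obtaining 68 scanned patients needs 68/(1 − f) attempts: 68/0.95 = 71.6, so 72; 68/0.90 = 75.6, so 76; 68/0.85 = 80. If failures were instead counted inside the 68, the scanned number would be 64.6, 61.2 or 57.8. After the loss the plan can absorb (54/68 = 79% retained), about 51, 49 or 46 would be evaluable, below 54.

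**The case against.** Accuracy among patients who can be scanned is a legitimate and openly restricted quantity, and a patient without a Qcsa value cannot inform the relation between Qcsa and outcome, which is the primary objective. Both named examples, amputation and edema, may be visible before scanning, and the protocol does not say when the criterion is applied. Ultrasound is proposed for use where communication fails, so scoring a failed scan as not flagged describes no pathway in the protocol. Much of this stands. It is why the scanned-patient analysis should remain the main one and why both conventions should be shown. It does not justify leaving failures uncounted, because the open wording also covers scans that are tried and fail.

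Four stronger readings are tempting and are not supported:

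- **That the reported accuracy is biased.** The restriction limits to whom the figures apply. It need not distort them among scanned patients.
- **That failures fall in sicker patients.** Edema is plausible in the nephrology and gastrointestinal/liver patients admitted, but the documents give neither its frequency nor its link to outcome.
- **That the comparison with APOP is one-sided.** The exclusion removes a patient from the evaluation of both tools, and Section 4 notes that APOP can draw on a caregiver. The documents give no rule for an APOP that cannot be obtained, so its handling is unknown.
- **That the study would miss its 0.8 level.** Starting from exactly 0.80, any failure takes one measure below it. From 0.90 the lowered measure would be 0.855, 0.81 or 0.765. The level in Section 5.9 is also a sample-size assumption, not a criterion for accuracy with failures included.

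**Conclusion.** The point holds as a question of applicability. As written, the plan can show how well Qcsa separates cases from non-cases among scannable patients. It cannot show how well the tool would serve older ED patients generally, because the failure rate and the outcomes of patients with failed scans are not collected as part of the study. Usefulness in the wider population may be overstated; the amount is unknown, and it is zero if no scan fails. At assumed failure rates of 5% to 15%, with 0.80 for both measures in scanned patients, one measure falls to between 0.76 and 0.68 and the other rises to between 0.81 and 0.83. Which one falls depends on how a failed scan is treated. The change is worth making because it is cheap and brings the conclusion into line with the trial's own question.

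**What to change.** - Limit the exclusion to conditions recognised before scanning, such as amputation and the existing paresis/paralysis criterion. State how edema is handled, and count those patients either way.
- Keep consenting patients with an attempted but failed scan in the cohort. Log the reason at the time, since an unlogged failure may not be recoverable later.
- Report the failure rate and these patients' outcomes, using the three-month and one-year follow-up that Acutelines already collects.
- Keep accuracy in scanned patients as the main analysis. Add a supplementary analysis with failed scans counted as test-negative and then as test-positive, giving sensitivity and specificity each time.
- Handle an unobtainable APOP the same way in the comparison.
- Keep 68 as the number of scanned patients and count failures in addition to it.

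Cost: a wording change, a short log and a little more analysis. About 72, 76 or 80 patients would be attempted at failure rates of 5%, 10% or 15%, but the current rule would require the same number to be approached in order to reach 68. The supplementary figures will be less favourable on one measure.
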